## **2.2. Visit Windows**

Nominal visits will be used for all by-visit analyses in the study. The study visits scheduled post randomization should occur at the times delineated in the Schedule of Activities. The study visits through Week 36 should occur within  $\pm 3$  days of the scheduled visit. The sponsor must be contacted for any significant deviation in the scheduling of a visit outside the appropriate window and determine how the subject should resume his/her normal dosing schedule relative to the baseline visit (Week 0).

## **2.3. Pooling Algorithm for Analysis Centers**

Unless otherwise specified, data from all investigational centers/sites will be pooled for analyses.

## 2.4. Analysis Sets

There will be two database locks at Weeks 16 and 36 respectively.

### **Week 16 database lock**

Week 16 database lock will include selected efficacy, safety, and PK data through Week 16 for all randomized and treated participants. The data will be primarily used in planning for future bermekimab clinical development in AD. The selected efficacy and safety data include but are not limited to the following:

1. Eczema Area and Severity Index (EASI)
2. Investigators Global Assessment (IGA) score
3. Itch Numeric Rating Scale (NRS) score
4. Pain Numeric Rating Scale (NRS) score
5. Baseline Disease Characteristics for 1-4 above
6. Demography
7. AE
8. PK

### **Week 36 database lock**

Week 36 DBL would include all data through Week 36 for all randomized and treated participants.

#### **2.4.1. Efficacy Analysis Set(s)**

##### **2.4.1.1. Full Analysis Set**

The full analysis set (FAS) population includes all randomized participants who received at least 1 dose of study agent. This analysis set will be used for the efficacy analyses of the endpoints through Week 36, *unless otherwise specified*.

In the efficacy analyses, participants will be analyzed according to the randomized treatment groups they were assigned to, regardless of the treatments they actually received.

##### **2.4.1.2. Per Protocol Analysis Set**

The primary endpoint will also be analyzed using the per-protocol population, which includes participants who are generally compliant with the protocol.

Specifically, the per protocol population includes participants in FAS except those

- who did not meet the inclusion criteria in the protocol as listed below:
  - EASI score  $\geq 16$  at screening and baseline visits.
  - IGA score  $\geq 3$  at screening and baseline visits.
  - $\geq 10\%$  body surface area (BSA) of AD involvement at screening and baseline visits.

- NRS Weekly Average of worst daily Skin Itch Scores at least 3 at screening
- who did not receive all scheduled study agent administrations prior to Week 16.

However, for those who discontinued the study agent prior to Week 16 will be included in the per protocol analysis and the data handling rule specified in section 5.2.2 will apply.

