## 4. ELIGIBILITY CRITERIA

### 4.1 INCLUSION CRITERIA

**No waivers/exemptions will be granted for protocol inclusion/exclusion criteria.**

Subjects are included in the study if they meet all of the following criteria:

- Written informed consent provided by the patient.
- Male or female, at least 18 years.
- Willing and able to attend all clinic visits and comply with study-related procedures
- Is able to understand and complete study-related questionnaires
- Chronic atopic dermatitis present for at least 3 years.
- EASI score  $\geq 16$  at screening and baseline visits.
- IGA score  $\geq 3$  at screening and baseline visits.
- Baseline pruritis numerical rating scale average score for maximum intensity of at least 3, based on the average of daily pruritis numerical rating scale scores for maximum itch intensity reported during the 7 days prior to randomization.
- Has applied a stable dose of topical moisturizer twice daily for at least 7 consecutive days immediately prior to the baseline visit and is willing to continue this regimen on a daily basis for the duration of the study.
- $\geq 10\%$  body surface area (BSA) of AD involvement at screening and baseline visits.
- Documented recent history (within 6 months prior to screening) of inadequate response to treatment with topical medications, or patients for whom topical treatments are medically inadvisable (because of important side effects or safety risks).
  - a) Inadequate response is defined as failure to achieve and maintain remission or a low disease activity state (comparable to an IGA score of 0-2), despite treatment with a daily regimen of topical corticosteroids of medium to higher potency (with or without topical calcineurin inhibitors as appropriate), applied for at least 28 days or for the maximum duration recommended by the product prescribing information, whichever is shorter.
  - b) Patients with documented systemic treatment for atopic dermatitis in the preceding 6 months are also considered to be inadequate responders to topical treatments and are potentially eligible for treatment with bermekimab, after appropriate washout.
  - c) Important side effects or risks are those that outweigh the potential treatment benefits, and include: intolerance to treatment, hypersensitivity reactions, significant skin atrophy, and adverse systemic effects.

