## 4.2 EXCLUSION CRITERIA

Subjects with ANY of the following will be excluded from the study:

- Age below 18 years as the current study is evaluating bermekimab in adult patients only
- Subject has been treated for AD with any investigational drug of chemical or biologic nature within a minimum of 30 days or 5 half-lives (whichever is longer) of the drug prior to baseline
- Treatment with bermekimab at any time in the past.
- Treatment with immunosuppressive/immunomodulatory drugs or phototherapy for atopic dermatitis within 4 weeks of baseline, or any condition that, in the opinion of the investigator, is likely to require such treatment(s) during the first 4 weeks of study treatment
- Treatment with topical corticosteroids or topical calcineurin inhibitors for the treatment of AD within 14 days prior to baseline]
- Treatment with biologics as follows:
  - a) Any cell-depleting agents including, but not limited to, rituximab, within 5 half-lives (if known) or 30 days prior to baseline visit, or until lymphocyte count returns to normal, whichever is longer.
  - b) Other biologics: within 5 half-lives (if known) or 30 days prior to baseline visit, whichever is longer
- Initiation of treatment of atopic dermatitis with prescription moisturizers or moisturizers containing additives such as ceramide, hyaluronic acid, urea, or filaggrin degradation products during the screening period (patients may continue to use stable doses of such moisturizers if initiated before the screening visit)
- Regular use (more than 2 visits per week) of a tanning booth/parlor within 4 weeks of the screening visit
- Planned or anticipated use of any prohibited medications and procedures during study treatment
- Treatment with a live (attenuated) vaccine within 30 days prior to the screening visit
- Active chronic or acute infection requiring treatment with systemic antibiotics, antivirals, antiparasitics, antiprotozoals, or antifungals within 2 weeks prior to the baseline visit, or superficial skin infections within 1 week prior to the baseline visit. NOTE: patients may be rescreened after infection resolves

- Known or suspected history of immunosuppression, including history of invasive opportunistic infections (e.g., tuberculosis, histoplasmosis, listeriosis, coccidioidomycosis, pneumocystis, aspergillosis) despite infection resolution; or unusually frequent, recurrent, or prolonged infections, per investigator judgment.

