## 4.5. Protocol Deviations

In general, the following list of major protocol deviations may have the potential to impact participants' rights, safety or well-being, or the integrity and/or result of the clinical trial. Participants with major protocol deviations will be identified prior to database lock and will be summarized by category by treatment group through Week 16 and Week 36 for the FAS.

- Entered study and did not satisfy entry criteria
- Received wrong treatment or incorrect dose
- Received excluded concomitant or non-drug therapy
- Out of window visit
- Out of window procedure
- Other

A listing of participants with major protocol deviations and a listing of patients who missed scheduled study agent administration will also be provided by randomized treatment group. In addition, analyses of COVID-19 related protocol deviations will be provided.

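### The per-protocol set is a closed list not linked to the SAP's own major deviations, so wrong-agent patients, washout breachers and users of prohibited non-rescue AD therapy can stay in it

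*SAP*

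**What the plan says.** The per-protocol set exists only in the SAP; protocol 10.3 defines a safety set and an mITT set. SAP 2.4.1.2 states the purpose first: a population "which includes participants who are generally compliant with the protocol". The operative sentence follows: "Specifically, the per protocol population includes participants in FAS except those". Two groups are then removed:

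- those "who did not meet the inclusion criteria in the protocol as listed below", with four criteria listed: EASI, IGA, BSA and itch;
- those who did not receive every scheduled administration before Week 16. Discontinuers are put back in under the data handling rule.

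SAP 4.5 lists major deviations that may affect patients' rights or safety, or the integrity or result of the trial. They include any unmet entry criterion, "Received wrong treatment or incorrect dose" and "Received excluded concomitant or non-drug therapy". They are to be identified before database lock, and are then summarised and listed.

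Protocol 4.2 excludes, among others, patients with "Treatment with topical corticosteroids or topical calcineurin inhibitors for the treatment of AD within 14 days prior to baseline", and those given immunosuppressive or immunomodulatory drugs or phototherapy for AD within 4 weeks of baseline.

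SAP 5.3.7 runs the primary estimand on the per-protocol set under the rules of SAP 5.3.3. There, only treatment discontinuation or a missing Week 16 EASI makes a patient a non-responder.

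**The concern.** The stated purpose and the operative list do not match. The SAP names deviations serious enough to affect the trial's result, has them identified before lock, and then leaves them out of the one population meant to represent compliance.

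No other planned analysis fills the gap. The two supplementary estimands in SAP 5.3.2 and 5.3.5 change only how treatment discontinuation and missing data are handled. The per-protocol analysis is therefore the only planned check of EASI-75 in compliant patients. If prohibited co-treatment or dosing errors had moved the comparison, it could not show this, because the patients concerned would still be in it.

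**Working it through.** **Is the list closed?** SAP 2.4.1.2 introduces its exclusions as a specification. It has no wording that leaves the list open and no reference to SAP 4.5. Where this SAP wants an open list it says so, as in the subgroups of 2.5 and the Week 16 lock contents in 2.4. The list is closed.

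**Who stays in, and can they be responders?**

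| Deviation | Where it appears | Removed by SAP 2.4.1.2? | Can be an EASI-75 responder under SAP 5.3.3? |
|---|---|---|---|
| Wrong agent or incorrect dose, all visits dosed | SAP 4.5 major deviation | Not clearly; only missed doses are named | Yes, in the randomised arm |
| Breach of an AD-therapy washout | Protocol 4.2; unmet entry criterion under SAP 4.5 | No; only four inclusion criteria are tested | Yes |
| Non-rescue topical corticosteroid or calcineurin inhibitor | Prohibited by protocol 2.10, which lets dosing continue after topical use | No | Yes |
| Phototherapy | Prohibited by protocol 2.10; not on its discontinuation list | No | Yes |
| Systemic corticosteroid or immunosuppressant, live vaccine, other investigational drug through Week 16 | Protocol 2.10 discontinuation list | No; discontinuers are kept | No; counted as non-responder |

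**Does the missed-dose criterion catch a wrong agent?** It could be read that way. But SAP 4.3 treats an incorrect agent or dose as a measure additional to receipt of each scheduled treatment, and SAP 7.1.1.1 lists an incorrect agent apart from a skipped administration when excluding PK data. The better-supported reading is that SAP 2.4.1.2 does not cover it.

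**Size.** The plan gives no figure for the per-protocol set. Its sample size does reproduce, though the point does not rest on it. For 60% v 20%, two-sided 0.05, 80% power:

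n = [1.96·√(2·0.4·0.6) + 0.842·√(0.6·0.4 + 0.2·0.8)]² / 0.4² = 22.3, so 23 per arm and 69 in all (power 81.2%).

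About 90 patients at 1:1:1 gives 30 per arm. With k responders among 30:

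- Removing one responder changes the rate by k/30 − (k−1)/29 = (30−k)/870. At k = 6 (20%) this is 2.8 points; at k = 18 (60%) it is 1.4 points.
- Removing one non-responder changes it by k/29 − k/30 = k/870. At k = 6 this is 0.7 points; at k = 18 it is 2.1 points.
- The largest change in either case is 29/870 = 1/30 = 3.3 points.

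The direction depends on the arm and on whether the deviator responded. The documents give no rate for any of these deviations, so the per-patient bound cannot be turned into an expected total.

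**Cost in precision.** Suppose, as an assumption, that 10%, 20% or 30% of 30 per arm were excluded. Then 27, 24 or 21 remain, and power at 60% v 20% is 87.3%, 82.9% or 77.4%, against 90.6% at 30. The 60% and 20% are the plan's ITT assumptions, used here only for scale.

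**The case against.** The strongest case against runs as follows. The per-protocol analysis is supportive, no decision rule uses it, and the choice of deviations that define it is partly a matter of design. The patients are not hidden: SAP 4.5 summarises and lists major deviations by arm, and SAP 4.6 lists everyone who received a concomitant treatment that could improve AD. Most on-study topical use would probably be recorded as rescue, which protocol 2.11 leaves to the investigator's discretion, so the group at issue may be small. And excluding patients for treatment taken after randomisation selects on something related to outcome: placebo patients doing badly are the likeliest to seek other therapy, so removing them need not recover an unbiased difference.

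All of this limits the point without removing it. Listings show who deviated but give no treatment comparison without them. The selection argument is a reason to read the result beside the FAS, not to leave the definition at odds with its stated purpose.

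Three stronger readings are tempting and are not supported.

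- A reader might infer that anyone on prohibited therapy can count as a compliant responder. Protocol 2.10 stops study drug for the agents in the last row of the table, and SAP 5.3.3 then makes those patients non-responders.
- A reader might assume deviation rates and calculate a loss of many points from the 40-point planning difference. No such rates are given, and the 60% and 20% are ITT assumptions, not rates in compliant patients. If the assumed users were rescue patients, this fix would leave them in the set anyway.
- A reader might infer that the itch criterion tests a different value from the one that qualified the patient, since the SAP has "NRS Weekly Average of worst daily Skin Itch Scores at least 3 at screening" while the protocol's criterion is "based on the average of daily pruritis numerical rating scale scores for maximum itch intensity reported during the 7 days prior to randomization". But protocol section 5 and its calendar place randomisation within screening, so those 7 days can fall in the screening period. This is wording to align, not a demonstrated second threshold.

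**Conclusion.** The point holds in limited form. SAP 2.4.1.2 does not deliver the compliant population that it describes, because its closed list ignores deviations that SAP 4.5 itself classes as major. Three groups are affected: wrong agent or incorrect dose (on the better-supported reading of the missed-dose criterion), breaches of the protocol 4.2 AD-therapy washouts, and prohibited non-rescue AD therapy that leaves dosing in place.

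The size is at most about 3.3 points in an arm's rate per retained deviator, assuming about 30 per arm; no total shift should be claimed. The primary FAS analysis does not change. This is a defect in a supportive analysis, worth correcting because the correction is cheap.

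**What to change.** In SAP 2.4.1.2, also exclude participants who, before the Week 16 EASI, have a SAP 4.5 major deviation in the categories "Received wrong treatment or incorrect dose" or "Received excluded concomitant or non-drug therapy" (the latter for non-rescue use), and participants who entered in breach of a protocol 4.2 AD-therapy washout. Adjudicate membership blind and finish before the Week 16 lock, because SAP 1.5.2 unblinds some sponsor staff at that point.

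Handle permitted rescue as in the main analysis. Protocol 10.5.3.1 counts rescued patients as non-responders, while SAP 5.3.2 treats rescue as part of the regimen. That is a separate conflict, and the two passages must be reconciled. Align the itch wording with protocol 4.1 in the same edit.

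The cost is a few sentences of SAP text. No new data are needed, since SAP 4.5 already has the deviations identified before lock. However, the open list of Week 16 lock contents in SAP 2.4 does not name deviations or concomitant medication, so both must be ready by then. The set becomes smaller and is partly selected on treatment taken after randomisation, so report it beside the FAS result and not as a replacement for it.

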#### **2.4.2. Safety Analysis Set**

The safety analysis set includes all randomized participants who received at least 1 dose of study agent, i.e., the treated population.

#### **2.4.3. Pharmacokinetics Analysis Set**

The pharmacokinetic (PK) analysis set includes all participants who received at least 1 dose of bermekimab and had at least 1 valid blood sample drawn for PK analysis after their first dose of bermekimab.

#### **2.4.4. Pharmacodynamics Analysis Set**

The Pharmacodynamics (PD) analysis set includes all participants who received at least 1 dose of bermekimab and had at least 1 valid blood sample drawn for PD analysis after their first dose of bermekimab.

#### **2.4.5. Immunogenicity Analysis Set**

The immunogenicity analysis set includes all participants who received at least 1 dose of bermekimab and who have at least 1 sample obtained after their first dose of bermekimab for the detection of antibodies to bermekimab.

### **2.5. Definition of Subgroups**

To evaluate the consistency in the primary efficacy endpoint (proportion of participants who achieve EASI-75 at Week 16) over demographics, baseline disease characteristics, and prior and baseline medication use, subgroup analyses will be performed when sample sizes are permitted. The subgroups include, but are not limited to, the following:

#### **Baseline demographics:**

- Sex (male, female)
- Race
- Baseline Age (<40 years, 40 to <65 years, ≥65 years)
- Baseline weight (≤80 kg, >80 kg)
- BMI (Normal [<25], Overweight [25 -<30], Obese [≥ 30])

**Baseline disease characteristics and AD medication:**

- Age at diagnosis (years) (< median, ≥ median)
- AD disease duration (years) (< median, ≥ median)
- Baseline EASI severity (less severe [EASI <28] or more severe [EASI ≥28])
- Baseline IGA (3, 4)
- Baseline C-reactive protein (CRP) (< median, ≥ median)
- Baseline Erythrocyte Sedimentation Rate (ESR) (< median, ≥ median)
- Prior biologic therapy (Yes/No)

**2.6. Study Day and Relative Day**

Study day is defined as the number of days from the study reference date to the event/visit date. It will be calculated as follows:

- If the event/assessment occurs on or after the reference date, then study day = event/assessment date – reference date + 1.
- If the event/assessment occurs before the reference date, then study day = event/assessment date – reference date.

Hence, the day of reference date is Study Day 1; the previous day is Study Day -1.

**2.7. Baseline and Endpoint**

In general, the baseline measurement is defined as the closest measurement taken prior to or at the time of the first study agent administration date unless otherwise specified.

**3. INTERIM ANALYSIS AND DATA MONITORING COMMITTEE REVIEW**

No interim analysis or data monitoring committee review is planned for this study.

**4. SUBJECT INFORMATION**

Unless specified otherwise, FAS will be used for the subject information analyses and participants will be analyzed according to the treatment group to which they were randomized, regardless of the treatment they actually received. The number of participants in each analysis set will be summarized by treatment group and overall.

Simple descriptive statistics, such as mean, median, standard deviation, interquartile range, maximum, and minimum for continuous variables, and counts and percentages for discrete variables will be used to summarize most data and no formal hypothesis testing for treatment comparisons will be performed. In addition, subject listings will also be used to present the data.

## 4.1. Demographics and Baseline Characteristics

The FAS will be used for all tabulations. Participants' demographic data and baseline disease characteristics will be summarized by treatment group. If imbalances are found at baseline, then additional analyses may be performed adjusting for baseline differences.

### 4.1.1. Demographic

Table 1 presents a list of the demographic variables that will be summarized by treatment group, and overall for the FAS.

**Table 1: Demographic Variables**

Continuous Variables:	Summary Type
Age (years)	Descriptive statistics (N, mean, standard deviation [SD], median and range [minimum and maximum], and IQ range).
Weight (kg)	
Height (cm)	
Categorical Variables:	
Age (<40 years, 40 to <65 years, and ≥65 years)	Frequency distribution with the number and percentage of participants in each category.
Sex (male, female)	
Weight (kg) (<= 80 kg, > 80 kg)	
Race (American Indian or Alaska Native, Asian, Black or African American, White, Other)	
Ethnicity (Hispanic or Latino, Not Hispanic or Latino)	
BMI (Normal [<25], Overweight [25 -<30], Obese [≥30])	

### 4.1.2. Baseline Disease Characteristics

Baseline disease characteristics (e.g., duration of AD disease, EASI score, GISS, POEM, SCORAD score, BSA, baseline IGA, NRS pain, NRS Itch, HADS, DLQI) will be summarized by treatment group.

### 4.1.3. Medical History

Summaries of participants' alcohol intake, and smoking status will be provided by treatment group. In addition, the distribution of participants by prior biologic use (yes/no) and type of biologic therapy will also be provided.

Medical history will be listed including body systems and condition/non-drug allergy as captured on the eCRF.

## 4.2. Disposition Information

The number of participants in the following disposition categories will be summarized by treatment group and overall:

- Participants screened: met the inclusion criteria regarding the target indication and signed the informed consent
- Participants randomized
- Participants randomized and received at least 1 study agent
- Participants who completed the study through Week 16 and Week 36
- Participants who discontinued study and the reasons for discontinuation through Week 16 and Week 36

Listings of participants will be provided for the following categories:

- Participants who discontinued study
- Participants who were unblinded during the study period

## 4.3. Treatment Compliance

Study agent compliance will be summarized descriptively through Week 16 and through the end of the study (Week 36) for the FAS. Number of the participants receiving each scheduled treatment will be summarized. In addition, treatment compliance will also be assessed by protocol deviations related to study agent administration (i.e., incorrect study agent or dose received).

